### 6.1 Cisplatin Dose Adjustments

- Ototoxicity: If hearing loss occurs, analysis of the risk of additional hearing loss versus the potential benefit of continuing cisplatin should be made. An audiogram may be obtained at the investigator’s discretion.
- Nephrotoxicity: If, despite adequate hydration, serum creatinine increases to > grade 1 ( $\geq 1.5 \times$  ULN), creatinine clearance should be recalculated before the next cisplatin dose and subsequent dose reductions will be recommended as follows:

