#### 3.1 Eligibility Criteria

Patients must have baseline evaluations performed prior to the first dose of study drug and must meet all inclusion and exclusion criteria. Results of all baseline evaluations, which assure that all inclusion and exclusion criteria have been satisfied, must be reviewed by the Principal Investigator or his/her designee prior to enrollment of that patient. In addition, the patient must be thoroughly informed about all aspects of the study, including the study visit schedule and required evaluations and all regulatory requirements for informed consent. The written informed consent must be obtained from the patient prior to enrollment. Patients eligible for enrollment in the treatment phase of this study **must meet all** of the following criteria:

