#### 3.2 Inclusion Criteria

1. Patients with stage III/IV per tumor/nodes/metastasis (TNM) guidelines for head and neck sites (American Joint Committee on Cancer [AJCC] 7th Edition), locally advanced, biopsy proven squamous cell cancer of the head and neck that undergo chemoradiation as their primary treatment with curative intent. Patients with oropharynx (HPV positive and HPV negative), hypopharynx, larynx primaries, nasopharynx as well as those with documented SCC of the cervical lymph nodes, with unknown primaries, are eligible.
2. >10 pack years of tobacco use or more
3. Age  $\geq$  18 years
4. ECOG performance status  $\leq$  2 (Appendix A)
5. Patients must have at least one site of measurable disease [if applicable] (per RECIST 1.1 for solid tumors or the appropriate disease classification/criteria for the target population)
6. Adequate bone marrow function as shown by: ANC  $>$   $1.5 \times 10^9/L$ , Platelets  $>$   $100 \times 10^9/L$ , Hb  $>$ 9 g/dL
7. Total calcium (corrected for serum albumin) within normal limits (biphosphonate use for malignant hypercalcemia control is not allowed)
8. Magnesium  $\geq$  the lower limit of normal
9. Potassium within normal limits for the institution.
10. Alanine aminotransferase (ALT) and aspartate aminotransferase (AST) within normal range
11. Serum bilirubin within normal range (or  $\leq 1.5 \times$  ULN if liver metastases are present; or total bilirubin  $\leq 3.0 \times$  ULN with direct bilirubin within normal range in patients with **well documented** Gilbert Syndrome)
12. Serum creatinine  $\leq 1.5 \times$  ULN or 24-hour clearance  $\geq 50$  mL/min
13. Serum amylase  $\leq$  ULN
14. Serum lipase  $\leq$  ULN
15. Fasting plasma glucose  $\leq 120$  mg/dL (6.7 mmol/L)
16. Signed informed consent

17.  $INR \leq 2$

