### 3.3 Exclusion criteria

Patients eligible for enrollment into the treatment phase of this study **must not meet any** of the following criteria:

1. Presence of distant metastatic disease
2. Less than or equal to 10 pack years of tobacco history
3. Patients who have received prior chemotherapy
4. Patients who have received prior radiation to the head and neck or adjacent anatomical site (e.g., upper lobe lung, brain)
5. Patients who have received prior treatment with a P13K inhibitor.
6. Patients with a known hypersensitivity to BKM120 or to its excipients
7. Patients with acute or chronic liver, renal disease or pancreatitis
8. Patients with the following mood disorders as judged by the Investigator or a psychiatrist, or as a result of patient's mood assessment questionnaire:
  - Medically documented history of or active major depressive episode, bipolar disorder (I or II), obsessive-compulsive disorder, schizophrenia, a history of suicidal attempt or ideation, or homicidal ideation (immediate risk of doing harm to others) or patients with active severe personality disorders (defined according to DSM- IV) are not eligible. **Note: for patients with psychotropic treatments ongoing at baseline, the dose and the schedule should not be modified within the previous 6 weeks prior to start of study drug.**
  - $\geq$  CTCAE grade 3 anxiety
  - Meets the cut-off score of  $\geq 12$  in the PHQ-9 or a cut-off of  $\geq 15$  in the GAD-7 mood scale, respectively, or selects a positive response of "1, 2, or 3" to question number 9 regarding potential for suicidal thoughts in the PHQ-9 (independent of the total score of the PHQ-9)
9. Patients with diarrhea  $\geq$  CTCAE grade 2
10. Patient has active cardiac disease including any of the following:
  - Left ventricular ejection fraction (LVEF)  $< 50\%$  as determined by Multiple Gated acquisition (MUGA) scan or echocardiogram (ECHO)
  - QTc  $> 480$  msec on screening ECG (using the QTcF formula)
  - Angina pectoris that requires the use of anti-anginal medication
  - Ventricular arrhythmias except for benign premature ventricular contractions
  - Supraventricular and nodal arrhythmias requiring a pacemaker or not controlled with medication
  - Conduction abnormality requiring a pacemaker
  - Valvular disease with document compromise in cardiac function
  - Symptomatic pericarditis
11. Patient has a history of cardiac dysfunction including any of the following:

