### **5.8.2 Cisplatin Treatment**

Commercially available supplies of cisplatin will be used for this study. Preparation instructions can be found in the FDA approved package insert. Cisplatin will be administered per institutional guidelines.

Cisplatin injection is a sterile, aqueous solution, available in 50ml, 100ml, and 200ml, multiple dose vials, each ml containing 1mg of Cisplatin and 9mg sodium chloride in water for injection. HCl and/or sodium hydroxide added to adjust pH to 3.5 to 4.5. It will be given intra-venously (IV) on days: (1, 8, 15, 22, 29, 36 and 43).

If radiation is held, BKM120 and cisplatin will be held as well. Additional weekly chemotherapy treatments may be added to the treatment course if chemo/XRT was held during the course of treatment. Cisplatin should be given only if at least 3 more days of radiotherapy treatment remain. Days of chemotherapy may be changed (+/-) 2 days if unforeseen circumstances require the timing of treatment. Treatment doses are based on body surface area (BSA). The actual body weight will be used for dose calculations as long as the BSA is below 2. For a BSA above 2, the BSA will be capped at 2.

Cisplatin is nephrotoxic and the patients will receive pre-and post treatment hydration according to institutional standards.

Institutional guidelines for highly emetogenic regimens will be followed. Patients will receive a 5HT antagonist for primary prevention of nausea and vomiting and will also receive 8 mg of dexamethasone IV according to institutional standards. The patients may receive a 5HT antagonist and decadron per IV on day 2 and 3 after chemotherapy for delayed nausea at the discretion of the investigator. The concomitant use of aprepitant and BKM120 is not allowed.

- Possible side effects of cisplatin are
  - Hematologic: Neutropenia, anemia, thrombocytopenia
  - Gastrointestinal: Nausea, vomiting
  - Dermatologic: Alopecia
  - Renal: Elevation of blood urea nitrogen (BUN) and Creatinine, hypomagnesemia, hypokalemia, hypocalcemia
  - Neurologic: Peripheral neuropathy, restlessness
  - Allergic reactions
  - Ototoxicity

Cisplatin is a commercially available product that is provided as part of standard of care.

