#### Dose Modification of Cisplatin in Kidney Impairment

Creatinine Clearance (mL/min)*	Cisplatin Dose**
$\geq 60$	100%
$\geq 40$ but $< 60$	50%
$< 40$	0%

\* Creatinine clearance as calculated by Cockcroft-Gault equation.

\*\* Percent dose reduction is calculated from the original dose, not the previous dose. If creatinine clearance recovers, the dose of cisplatin should be re-escalated to the patient’s previous dose level as is outlined in the Dose Modification of Cisplatin in Kidney Impairment chart above. There is no maximum limit.

Serum creatinine will be measured weekly within 24 hours of cisplatin dosing.

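### Below creatinine 1.5 x ULN the protocol requires no estimated clearance at entry or before cisplatin, so some lighter, older or female patients could get full-dose cisplatin at an estimated clearance below 40 mL/min

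*Combined protocol and SAP*

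**What the plan says.** Entry. Inclusion 12 in section 3.2 is an either/or rule, joined by "ULN or 24-hour clearance": creatinine no higher than 1.5 x ULN, or a 24-hour clearance of at least 50 mL/min. The creatinine arm suffices alone and carries no clearance floor. Section 3.3, item 7, bars "Patients with acute or chronic liver, renal disease or pancreatitis" without a threshold. Section 3.1 says baseline results "must be reviewed by the Principal Investigator or his/her designee prior to enrollment of that patient".

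On treatment. The section 6.1 trigger is "Nephrotoxicity: If, despite adequate hydration, serum creatinine increases to > grade 1", with 1.5 x ULN or more given in parentheses. Then "creatinine clearance should be recalculated before the next cisplatin dose", and reductions are recommended from a chart: 100% at 60 mL/min or above, 50% from 40 to below 60, and 0% below 40. A footnote specifies "Creatinine clearance as calculated by Cockcroft-Gault equation", and a line below the chart adds "Serum creatinine will be measured weekly within 24 hours of cisplatin dosing".

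Elsewhere. Section 5.8.2 says "Cisplatin will be administered per institutional guidelines". The chemistry panels in section 5.12.1.4 and Table 17 list creatinine but no clearance. Table 17 marks serum chemistry at screening, CRT day 1 and end of treatment only. The creatinine thresholds in Tables 9 and 10 begin at 2.0 x ULN, later than the section 6.1 trigger.

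**The concern.** The entry rule and the dosing trigger both run on serum creatinine as a multiple of ULN, while the dosing chart runs on estimated clearance. Clearance also depends on age, weight and sex, and eligibility sets no upper age limit and no weight limit. A small or elderly patient can therefore be well below 40 mL/min before creatinine reaches the point at which anyone is told to calculate it.

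The stake is patient safety. Section 5.8.2 itself calls cisplatin nephrotoxic. A site following only the explicit numerical rules could give a full dose at a clearance for which the protocol's own nephrotoxicity chart recommends none.

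**Working it through.** **Inputs from the protocol:** the 1.5 x ULN limit (inclusion 12 and section 6.1), the 40 mL/min row, and the Cockcroft-Gault method (section 6.1 chart). The plan states no figure here to reproduce.

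**Assumed inputs:** ULN 1.1-1.3 mg/dL for men and 0.9-1.1 for women; ages and weights as shown; actual body weight in the formula.

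**Formula:** clearance = (140 - age) x weight / (72 x creatinine), times 0.85 for women.

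**Entry examples**
- Man, 65 y, 60 kg, creatinine 1.75: 75 x 60 / (72 x 1.75) = 35.7 mL/min. At ULN 1.2 this is 1.46 x ULN, so the creatinine arm is met. At ULN 1.1 it is 1.59 x ULN, and it is not.
- Woman, 65 y, 55 kg, creatinine 1.40: 0.85 x 75 x 55 / (72 x 1.40) = 34.8 mL/min. At ULN 1.0 this is 1.40 x ULN, so the arm is met. At ULN 0.9 it is 1.56 x ULN, and it is not.

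**Window between clearance 40 and the trigger.** Clearance is 40 when creatinine = (140 - age) x weight / (72 x 40), times 0.85 for women. This gives 4500/2880 = 1.56 for the man and 3506.25/2880 = 1.22 for the woman.

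| Patient | ULN | 1.5 x ULN | Clearance there | Creatinine window below 40 mL/min |
|---|---|---|---|---|
| Man 65 y, 60 kg | 1.1 | 1.65 | 37.9 | 1.56-1.65 |
| | 1.2 | 1.80 | 34.7 | 1.56-1.80 |
| | 1.3 | 1.95 | 32.1 | 1.56-1.95 |
| Woman 65 y, 55 kg | 0.9 | 1.35 | 36.1 | 1.22-1.35 |
| | 1.0 | 1.50 | 32.5 | 1.22-1.50 |
| | 1.1 | 1.65 | 29.5 | 1.22-1.65 |
| Man 60 y, 75 kg | 1.2 | 1.80 | 46.3 | none (below 40 only from 2.08) |
| Woman 60 y, 75 kg | 1.0 | 1.50 | 47.2 | none (below 40 only from 1.77) |

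The window can close entirely. At ULN 1.0 the first man's clearance at 1.5 x ULN is 4500/(72 x 1.50) = 41.7.

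**Weight below which clearance is already under 40 at 1.5 x ULN** = 40 x 72 x 1.5 x ULN / (140 - age), divided by 0.85 for women.
- Men, ULN 1.2 (5184 / (140 - age)): 64.8, 69.1 and 74.1 kg at 60, 65 and 70 years.
- Women, ULN 1.0 (4320 / (0.85 x (140 - age))): 63.5, 67.8 and 72.6 kg.
- At 65 years over the assumed ULNs: 63.4-74.9 kg for men and 61.0-74.5 kg for women.

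**Grid** (ages 50-75 by 5 years; men 55-100 kg, women 45-90 kg, by 5 kg; 60 cells per sex). Cells below 40 mL/min at 1.5 x ULN number 11, 17 and 26 for men (ULN 1.1, 1.2, 1.3) and 22, 28 and 36 for women (ULN 0.9, 1.0, 1.1). Cells are equally weighted and are not shares of patients.

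**The case against.** The strongest reply is that the chart was never meant as a general clearance limit. It is a recommended response to a creatinine rise during treatment, and neither the 50% nor the 0% row is written to apply without that rise. This stands. A reader might infer that the protocol breaches its own stop rule, or that full dose at a clearance of 50 to below 60 is also an error. The documents support neither, and inclusion 12 itself accepts a measured clearance of 50.

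Second, meeting inclusion 12 is not enrolment. Exclusion 7 is mandatory, the investigator reviews baseline results, and both entry examples have creatinine at least 40% above the assumed ULN. An investigator might judge either patient to have renal disease. That is a real safeguard, but it has no threshold, and inclusion 12 expressly tolerates creatinine up to 1.5 x ULN. It may catch some patients; it cannot be relied on to catch all.

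Third, institutional cisplatin guidelines could require an earlier calculation, and the word recalculated in section 6.1 suggests an earlier value. The guidelines are not in the documents, and no section asks for that value.

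Fourth, the CTCAE scale is cited but not reproduced, so an earlier on-treatment trigger than the parenthesis states cannot be ruled out. This weakens the on-treatment half. The entry half does not depend on it.

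**Conclusion.** The gap is real but conditional. As written, a patient can meet inclusion 12 and receive a first full dose of cisplatin with no estimated clearance on record, and for some lighter, older or female patients that clearance would be below 40 mL/min. Continuing at full dose below 40 is possible but less certain.

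The size depends on assumed ULN, age and weight, and the examples move with the ULN. Larger patients such as the 60-year-olds at 75 kg are unaffected. The documents give no basis for a frequency. It would go too far to say that such patients will be enrolled, or will be given full dose: exclusion 7 and local guidelines may prevent either. What is established is that no stated numerical rule does so. It should be fixed, because the consequence is a safety one and the input needed is already collected.

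**What to change.** 1. Inclusion 12: for patients entering on the creatinine arm, also require Cockcroft-Gault clearance of at least 40 mL/min, unless a measured 24-hour clearance is at least 50 mL/min.
2. Section 6.1: before each cisplatin dose, calculate Cockcroft-Gault clearance from the weekly creatinine already required. Below 40 mL/min, hold cisplatin even if creatinine is under 1.5 x ULN, unless a measured 24-hour clearance is at least 50 mL/min. Resume by the existing chart.
3. Table 17: show the weekly creatinine so that the calendar agrees with section 6.1. This is a consistency edit only.

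**Cost.** Amendment wording and one calculated field per dose; no new routine test. A few small or elderly patients become ineligible or miss doses, some at normal creatinine. With creatinine exactly at ULN, 0, 0 and 1 of 60 grid cells for men (ULN 1.1, 1.2, 1.3) and 1, 4 and 7 of 60 for women (ULN 0.9, 1.0, 1.1) are already below 40. In the extreme cell, a woman of 75 y and 45 kg, the hold would start just above creatinine 0.85 x 65 x 45 / 2880 = 0.86, which is why the measured-clearance override matters.

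Missed doses count against the cumulative 200 mg/m2 mark cited in section 2.3. Over seven planned doses, one hold at 30 mg/m2 leaves 30 x 6 = 180, two at 35 leave 35 x 5 = 175, and three at 40 leave 40 x 4 = 160. Section 5.8.2 allows weekly doses to be added after a hold, and section 5.1 keeps BKM120 and radiation going.

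**Left to the sponsor.** Below 1.5 x ULN this rule steps from 100% to 0% at 40 mL/min. Extending the 50% band would smooth the step, but it would halve curative-intent cisplatin at near-normal creatinine: a 60-year-old, 70 kg man falls below 60 mL/min from 80 x 70 / (72 x 60) = 1.30 mg/dL, or 1.08 x ULN at ULN 1.2. It would also blur dose levels 1 to 3, which differ only in cisplatin dose.

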#### Dose Modification of Cisplatin in Kidney Impairment

Creatinine Clearance (mL/min)*	Cisplatin Dose**
$\geq 60$	100%
$\geq 40$ but $< 60$	50%
$< 40$	0%

\* Creatinine clearance as calculated by Cockcroft-Gault equation.

\*\* Percent dose reduction is calculated from the original dose, not the previous dose. If creatinine clearance recovers, the dose of cisplatin should be re-escalated to the patient’s previous dose level as is outlined in the Dose Modification of Cisplatin in Kidney Impairment chart above. There is no maximum limit.

Serum creatinine will be measured weekly within 24 hours of cisplatin dosing.

#### Dose Modification of Cisplatin Based on ANC

ANC ( $\times 10^9/L$ ) within 24	Action to be taken

hrs of therapy	
≥ 1.5	Treat at current dose
≥ 1.0, < 1.5	Treat at 75% of cisplatin dose
< 1.0	Hold treatment, and resume therapy at 75% of cisplatin dose at the next weekly therapy planned when ANC ≥ 1.0. If neutropenia requiring further chemotherapy break occurs, cisplatin will be discontinued for the remainder of the therapy, and only BKM120 and radiation will be continued

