### **5. TREATMENT PLAN**

#### **5.1 Treatment Regimen**

The investigational therapy used in the course of this study is BKM120. Treatment with BKM120 starts 2 weeks prior to cisplatin and radiotherapy and continues until the end of radiotherapy.

Study medication will be self-administered by the patients continuously throughout radiation. In order to assure compliance with protocol procedures drug administration will be thoroughly explained to the patients. During the study, BKM120 will be administered orally. It is given every day including weekend days. Administration of BKM120 stops with the end of radiotherapy. If radiation is held due to toxicity, BKM120 and cisplatin will be held as well. If cisplatin is held due to toxicity, BKM120 and radiation will continue. If BKM120 is held due to toxicity, cisplatin and radiation will continue. Medication labels will comply with US legal requirements and be printed in English. The storage conditions for study drug will be described on the medication label.

BKM120 will be provided by Novartis Pharmaceuticals free of charge. BKM120 is formulated as capsules for oral administration of 10mg and 50mg strength. Capsules are packaged in bottles. BKM120 capsule cannot be crushed and has to be swallowed. It cannot be given via enteral feeding tube.

If vomiting occurs, no attempt should be made to replace the vomited dose.

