
a ≥ CTCAE grade 3 anemia will not be considered DLT unless judged to be a hemolytic process secondary to study drug. ≥ CTCAE grade 3 lymphopenia will not be considered DLT unless clinically significant.
 
b For any grade 3 or 4 hepatic toxicity that does not resolve within 7 days to ≤ grade 1 (or ≤ grade 2 if liver infiltration with tumor present), an abdominal CT scan has to be performed to assess if it is related to disease progression.
 
A single patient is assumed not to tolerate the dose if he/she experiences at least one DLT. If a lower grade AE leads to a dose interruption of more than 7 doses of BKM120, this AE will be considered as DLT.
 
If the 2nd occurrence of an initially non-dose limiting toxicity (e.g., grade 3 AST that resolved to ≤ grade 1 within 7 days at 1st occurrence) leads to a dose reduction ( Section 6) within 28 days of the first dose of BKM120, this will be considered a DLT.
	

The investigator must notify the sponsor immediately of any unexpected ≥ CTCAE grade 3 adverse events or laboratory abnormalities. Prior to enrolling patients into a higher dose level, ≥ CTCAE grade 2 adverse events will be reviewed for all patients at the current dose level.

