## 6. DOSING DELAYS/DOSE MODIFICATIONS

**Table 11: BKM120 dose level modification guidelines: Criteria for interruption and re-initiation of BKM120 treatment**

Recommended Dose Modifications for BKM120	
Worst toxicity (CTCAE Grade)**	Recommended Dose Modifications
No toxicity	Maintain dose level
HEMATOLOGICAL	
Neutropenia (ANC)	
Grade 1 (ANC < LLN – 1.5 x 10  /L) Grade 2 (ANC < 1.5 – 1.0 x 10  /L)	Maintain dose level
Grade 3 (ANC < 1.0 – 0.5 x 10  /L) Grade 4 (ANC < 0.5 x 10  /L)	Omit dose until resolved to ≤ Grade 1, then: 
 
• If resolved in ≤ 7 days, then maintain dose level
 
• If resolved in > 7 days, then ↓ 1 dose level
 

Febrile neutropenia (ANC < 1.0 x 10  /L, fever ≥ 38.5°C)	Omit dose until resolved, then ↓ 1 dose level
Thrombocytopenia	
Grade 1 (PLT < LLN – 75 x 10  /L) Grade 2 (PLT < 75 – 50 x 10  /L)	Maintain dose level
Grade 3 (PLT < 50-25 x 10  /L)	Omit dose until resolved to ≤ Grade 1, then: 
 
• If resolved in ≤ 7 days, then maintain dose level
 
• If resolved in > 7 days, then ↓ 1 dose level
 

Grade 4 (PLT < 25 x 10  /L)	Omit dose until resolved to ≤ Grade 1, then ↓ 1 dose level

Recommended Dose Modifications for BKM120	
Worst toxicity (CTCAE Grade)**	Recommended Dose Modifications
HEPATIC	
Bilirubin (*for patients with Gilbert Syndrome these dose modifications apply to changes in direct bilirubin only)	Will be fractionated if elevated
Grade 1 (> ULN – 1.5 x ULN)	Maintain dose level with LFTs* monitored as per protocol
Grade 2 (> 1.5 – 3.0 x ULN) with ALT or AST ≤ 3.0 x ULN	Omit dose until resolved to ≤ Grade 1, then: 
 
• If resolved in ≤ 7 days, then maintain dose level
 
• If resolved in > 7 days, then ↓ 1 dose level
 

Grade 3 (> 3.0 – 10.0 x ULN) with ALT or AST ≤ 3.0 x ULN	Omit dose until resolved to ≤ Grade 1, then: 
 
• If resolved in ≤ 7 days, ↓ 1 dose level
 
• If resolved in > 7 days discontinue patient from study treatment
 

Grade 4 (> 10.0 x ULN)	Omit dose and discontinue patient from study treatment
AST or ALT	
Grade 1 (> ULN – 3.0 x ULN)	Maintain dose level with LFTs* monitored as per protocol

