**Dose Modification of Cisplatin Based on Platelet Count**

Platelet count within 24 hrs of therapy	Action to be taken
≥100,000	Treat at current dose
< 100,000	Hold treatment, and resume therapy at 75% of cisplatin dose at the next weekly therapy planned when platelets are at or above 100,000. If thrombocytopenia requiring further chemotherapy break occurs, cisplatin will be discontinued for the remainder of the therapy, and only BKM120 and radiation will be continued.

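### Section 5.1 and the cisplatin count tables continue BKM120 during low counts at which Table 11 omits it; no passage says which governs, and in a narrow window DLT status can depend on it

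*Combined protocol and SAP*

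**What the plan says.** Two sets of instructions apply to BKM120 when a blood count is low enough to hold cisplatin.

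**Continue.** Section 5.1: "If cisplatin is held due to toxicity, BKM120 and radiation will continue". It carries no condition on grade or cause. In section 6.1, the ANC table holds cisplatin below 1.0 × 10⁹/L: "Hold treatment, and resume therapy at 75% of cisplatin dose at the next weekly therapy planned when ANC ≥ 1.0". If a further break is needed, "cisplatin will be discontinued for the remainder of the therapy, and only BKM120 and radiation will be continued". The platelet table holds cisplatin below 100,000 and ends the same way: "If thrombocytopenia requiring further chemotherapy break occurs, cisplatin will be discontinued for the remainder of the therapy, and only BKM120 and radiation will be continued".

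**Omit.** Table 11, for grade 3 or 4 neutropenia (ANC below 1.0) and for grade 3 thrombocytopenia (platelets below 50): "Omit dose until resolved to ≤ Grade 1, then" maintain the dose if recovery took 7 days or less, otherwise reduce one level. Grade 4 thrombocytopenia is also omitted until grade 1 or better. In Table 11, grade 1 begins at ANC 1.5 and platelets 75. Section 5.5 interrupts BKM120 for a DLT or potential DLT unless otherwise specified. Table 10 requires recovery to grade 1 or better before re-treatment.

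**Link to DLTs.** Table 9 counts grade 3 or higher neutropenia, and grade 3 thrombocytopenia, as a DLT only after more than 7 consecutive days. Its footnote adds: "If a lower grade AE leads to a dose interruption of more than 7 doses of BKM120, this AE will be considered as DLT".

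**The concern.** A site treating a patient whose ANC is 0.9 can find an instruction to keep giving BKM120 and another to omit it, with nothing to say which prevails. Neutropenia and thrombocytopenia are listed in section 5.8.2 as possible effects of cisplatin, so the situation is foreseeable.

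Two things are at stake. The first is safety and consistency: the investigational drug may be given or withheld through a grade 3 or 4 cytopenia depending on the page consulted. The second is the primary endpoint. The Table 9 footnote makes missed BKM120 doses a route to a DLT, so the order followed can itself affect the DLT count from which the MTD is derived. The limits of more than 14 days' delay (section 5.6) and of two dose reductions (section 5.7) also depend on which order was followed.

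**Working it through.** **1. The orders side by side**

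| Situation | Section 5.1 and the 6.1 count tables | Table 11 |
|---|---|---|
| ANC < 1.0, first break | Cisplatin held; the ANC table does not name BKM120; section 5.1 continues it | BKM120 omitted until ANC ≥ 1.5 |
| ANC < 1.0, further break | Cisplatin stopped; the ANC table continues BKM120 | BKM120 omitted until ANC ≥ 1.5 |
| Platelets < 50 | Cisplatin held or stopped; BKM120 continued (section 5.1, and the platelet table at a further break) | BKM120 omitted until platelets ≥ 75 |
| Platelets falling no lower than 50, but < 100 | Cisplatin held; BKM120 continued | BKM120 maintained: no conflict |

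The sentence after Table 11 about toxicity due to BKM120 does not settle the matter. It governs dose reduction, not omission, and neither count table has an attribution condition.

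**2. When the DLT result can differ**

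BKM120 is given daily, including weekends (section 5.1), so one day is one dose. Let *a* be the days at grade 3 or higher and *b* the following days at grade 2.

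- Table 11 followed: omitted doses = *a* + *b*; DLT if *a* > 7 or *a* + *b* > 7.
- Section 5.1 followed: omitted doses = 0; DLT only if *a* > 7.

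| *a* | *b* | Doses omitted under Table 11 | DLT, Table 11 | DLT, section 5.1 |
|---|---|---|---|---|
| 4 | 3 | 7 | no | no |
| 4 | 4 | 8 | yes | no |
| 7 | 1 | 8 | yes | no |
| 8 | 0 | 8 | yes | yes |

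The results differ only when *a* ≤ 7 and *a* + *b* > 7. Grade 3 platelets follow the same arithmetic. Grade 4 thrombocytopenia and febrile neutropenia are DLTs under either order.

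An illustrative (assumed) first-break course: ANC 0.9 on CRT day 22, 1.2 from day 26, 1.5 on day 32. Grade 3 covers days 22 to 25, 4 days, so the duration row is not met. Under Table 11, BKM120 is omitted on days 22 to 31: 4 + 6 = 10 doses, more than 7. Under section 5.1 none is omitted. Because this is a first break, continuation rests on section 5.1 alone.

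**3. Effect on the escalation decision**

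Under Table 7, one changed result moves 0/3 (escalate) to 1/3 (add three), 1/3 to 2/3 (stop), or 1/6 (escalate) to 2/6 (stop; the previous level is the MTD).

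Section 13's escalation probabilities reproduce from P(escalate) = (1 − p)³ + 3p(1 − p)² × (1 − p)³:

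- p = 20%: 0.512 + 0.197 = 0.709 (plan: .71)
- p = 30%: 0.343 + 0.151 = 0.494 (plan: .49)

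The documents do not give the share of patients in the window. Let *q* be an assumed share of otherwise DLT-free patients whose status turns on the order followed. The DLT rate under Table 11 is then p + (1 − p)q.

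| *q* | Rate from 20% | P(escalate) | Rate from 30% | P(escalate) |
|---|---|---|---|---|
| 0 | 20% | 0.709 | 30% | 0.494 |
| 5% | 24% | 0.622 | 33.5% | 0.425 |
| 10% | 28% | 0.536 | 37% | 0.360 |
| 20% | 36% | 0.378 | 44% | 0.248 |

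These rows show sensitivity only; they do not estimate *q*.

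**The case against.** The best answer is that each table governs its own drug. Section 6.1 adjusts cisplatin; Table 11 sets interruption and restart of BKM120. Section 5.1 also has a mirror sentence, "If BKM120 is held due to toxicity, cisplatin and radiation will continue". If both sentences were absolute, each drug would be held and continued at once whenever both tables called for a hold. They are better read as saying that a hold of one drug does not by itself hold the other. Section 5.14 refers BKM120 interruptions to Table 11, and section 5.5 and Table 10 point the same way. The statement in the cisplatin tables may only describe what remains of the regimen once cisplatin is dropped, not dosing through the current nadir.

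That reading is coherent, but the protocol does not state it. Section 5.1 has no exception for Table 11. The cisplatin tables are as count-specific as Table 11 and name BKM120 as continuing. Section 5.5 yields where something else is specified, which section 5.1 arguably does. Section 5.4, in wording close to that of section 5.14, refers interruptions to Table 9 instead.

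Several parts of the objection do stand against stronger readings that a reader might infer:

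- *That the cisplatin tables order BKM120 through any ANC below 1.0.* They name it only at a further break.
- *That opposite orders always produce opposite DLT results.* They do so only in the window shown. The footnote's lower-grade wording must also cover a short grade 3 event or its grade 2 tail. And if Table 9's row for other grade 3 or worse events is read to include blood counts, both orders give a DLT and the difference disappears, although the more-than-7-day count rows would then be redundant.
- *That the different restart thresholds (ANC 1.0 for cisplatin, 1.5 for BKM120) are a contradiction.* They concern two drugs, and section 5.1 allows cisplatin while BKM120 is held.
- *That any platelet count low enough to hold cisplatin conflicts.* Counts falling no lower than 50 do not.

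**Conclusion.** The conflict in orders holds on the literal text for ANC below 1.0 and platelets below 50: BKM120 is both continued and omitted, and precedence is not stated. It does not depend on any numerical assumption.

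The DLT consequence is conditional. It requires grade 3 or higher neutropenia, or grade 3 thrombocytopenia, lasting 7 days or less, with recovery to grade 1 taking more than 7 doses. It also requires that the event otherwise qualifies under section 5.5, that the footnote applies to it, and that the general grade 3 row does not cover counts. Within those limits, one patient is enough to change a Table 7 decision. How often this would happen cannot be derived from the documents. No view is taken here on which clinical rule is right.

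**What to change.** The sponsor should reconcile section 5.1, section 5.5, Table 10, Table 11 and the two cisplatin count tables in section 6.1, so that a single order applies to BKM120 during a cytopenia that also holds cisplatin, at a first break and at a further one. The choice of clinical rule is the sponsor's.

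The Table 9 footnote should state whether BKM120 doses omitted for a blood count that does not meet the hematologic DLT row count toward the more-than-7-doses rule. The same note could say whether the row for other grade 3 or worse events covers blood counts, since the answer depends on it.

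The cost is a few sentences in an amendment, with no added visits, tests or patients. If patients have already been treated, the cohort review should record which order was followed for each qualifying cytopenia, so that DLTs are scored consistently.
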